## 6 Treatment

### 6.1 Study treatment

#### 6.1.1 Investigational and control drugs

**Table 6-1 Investigational and control drug**

Investigational/ Control Drug	Pharmaceutical Dosage Form	Route of Administration	Supply Type	Sponsor (global or local)
Ensovibep 15 mg/mL for Part A	Solution for infusion	i.v.	Non-blinded vials	Sponsor (global)
Placebo for Part A	Solution for infusion	i.v.	Saline infusion bag	Sponsor (global)
Ensovibep 15 mg/mL for Part B	Solution for infusion	i.v.	Double-blind vials	Sponsor (global)
Placebo for Part B	Solution for infusion	i.v.	Double-blind vials	Sponsor (global)

The investigational drug is ensovibep.

The formulation for Part A is 15 mg/mL ensovibep provided in isotonic buffer matrix [REDACTED]

The formulation for Part B is 15 mg/mL ensovibep provided in isotonic buffer matrix [REDACTED]

Isotonic saline will be used as placebo for Part A of the study. For Part B [REDACTED]

#### 6.1.2 Additional study treatments

No other treatment beyond investigational drug and control drug are included in this trial.

### **6.1.3 Treatment arms/group**

#### **Part A**

Patients in Part A will be assigned on Day 1 at Visit 1 to one of the following 4 treatment arms in a ratio of 1:1:1:1 and will be dosed accordingly:

- Ensovibep 75 mg
- Ensovibep 225 mg
- Ensovibep 600 mg
- Placebo

#### **Part B**

Once the optimal safe and efficacious dose has been selected from Part A, patients in Part B will be assigned on Day 1 at Visit 1 to one of the following 2 treatment arms in a ratio of 1:1:

- Ensovibep (optimal safe and efficacious dose, selected in Part A)
- Placebo

### **6.2 Other treatments**

#### **6.2.1 Concomitant therapy**

Ongoing long-term medications should be continued and adjusted as needed for the management of underlying conditions.

Symptomatic therapy to manage COVID-19 symptoms, such as antipyretics, analgesics, or oxygen, is permitted. If local standard of care includes further medications tailored to prevent COVID-19 complications (e.g., anticoagulation), these may be used, with the exception of drugs that are immunomodulators (e.g., interferon, tocilizumab, sarilumab, colchicine), immunosuppressives (e.g., steroids) or antivirals. Patients will be required to get upfront approval from the investigator to start any new prescription, OTC, and herbal medication treatments, with the exception of paracetamol up to 3 g/day, which does not require upfront investigator approval.

All medications, procedures, and significant non-drug therapies (including physical therapy and blood transfusions) administered after the patient was enrolled into the study must be recorded on the appropriate Case Report Forms (CRFs). Prior concomitant therapy defined as all medications taken within 30 days prior to enrollment will also be recorded appropriately in the CRFs.

SARS-CoV-2 vaccinations must not be scheduled up to the Day 29 visit, and if possible, should be postponed to take place after completion of the study (Day 91 visit) as ensovibep may neutralize the effectiveness of the vaccine. If such vaccinations take place prior to the last visit, they need to be documented in the relevant electronic Case Report Form (eCRF).

Each concomitant drug must be individually assessed against all exclusion criteria/prohibited medication. If in doubt, the investigator should contact the medical monitor before randomizing a patient or allowing a new medication to be started.

### **6.2.2 Prohibited medication**

The following concomitant therapies are prohibited: SARS-CoV-2 antiviral medication (experimental or approved), including convalescent serum or anti-viral antibodies; immune-modulating (e.g., interferon, tocilizumab, sarilumab) or immunosuppressive (e.g., steroids) medications initiated for management of COVID-19. However, patients who use immunosuppressive drugs as long-term or chronic treatment for pre-existing conditions and are on a stable dose and regimen may continue to use them.

### **6.2.3 Rescue medication**

Study participants who have progression of their COVID-19 such that they require treatment at the discretion of the investigator or treating physician should receive appropriate medical care, which may include: Anti-SARS-CoV-2 antiviral medication (experimental or approved), including convalescent serum or anti-viral antibodies; immune-modulating (e.g., interferon, tocilizumab, sarilumab, and colchicine) or immunosuppressive (e.g., steroids) medications for management of COVID-19.

## **6.3 Patient numbering, treatment assignment, randomization**

### **6.3.1 Patient numbering**

Each patient is identified in the study by a Patient Number (Patient No.), that is assigned when the patient is enrolled for screening and is retained for the patient throughout his/her participation in the trial. A new Patient No. will be assigned at every subsequent enrollment if the patient is re-screened. The Patient No. consists of the Center Number (Center No.) (as assigned to the investigative site) with a sequential patient number suffixed to it, so that each patient's participation is numbered uniquely across the entire database. Upon signing the ICF, the patient is assigned to the next sequential Patient No. available.

### **6.3.2 Treatment assignment, randomization**

At Visit 1, all eligible patients will be randomized via Interactive Response Technology (IRT) to one of the treatment arms. The investigator or his/her delegate will contact the IRT after confirming that the patient fulfills all the inclusion/exclusion criteria. The IRT will assign a randomization number to the patient, which will be used to link the patient to a treatment arm and will specify a unique medication number for the preparation of investigational product (IP) infusion to be administered to the patient. There will be a blinded and unblinded access to the IP allocation from IRT depending on site staff role for Part A. Part B will be fully blinded.

The randomization numbers will be generated using the following procedure to ensure that treatment assignment is unbiased and concealed from patients and investigator staff. A patient randomization list will be produced by the IRT provider using a validated system that automates

the random assignment of patient numbers to randomization numbers. These randomization numbers are linked to the different treatment arms, which in turn are linked to medication numbers. A separate medication list will be produced using a validated system that automates the random assignment of medication numbers to vials containing the study treatment.

### **Stratification criteria**

Randomization will be stratified by risk of progression to severe COVID-19 and/or hospitalization: “high risk” or “not at high risk”. The stratum will be determined by the investigator according to below and entered into the interactive web response system (IWRS) at the time of randomization.

Patients will be considered “high risk” if they meet at least one of the following criteria:

- Have a body mass index (BMI)  $\geq 35$
- Have chronic kidney disease
- Have diabetes mellitus
- Have immunosuppressive disease
- Are currently receiving immunosuppressive treatment
- Are  $\geq 65$  years of age
- Are  $\geq 55$  years of age AND have
  - Cardiovascular disease, OR
  - Hypertension, OR
  - Chronic obstructive pulmonary disease/other chronic respiratory disease.

All patients not meeting the above high-risk criteria will be considered “not at high risk”.

### **6.4 Treatment blinding**

Site firewalls to prevent unblinding and fully dedicated unblinded clinical teams managing the study will be assigned to ensure that the unblinded treatment assignment, the unblinded IRT outputs, the unblinded treatment administration and handling are overseen in such a way as to ensure patient safety and protocol adherence without risking unblinding the site study staff and the clinical teams. Refer to Pharmacy Manual for IP handling.

This is a patient, investigator, and sponsor-blinded study. Patients, investigators, and the sponsor will remain blinded to study treatment throughout the study, except where indicated below.

The identity of the treatments will be concealed by the use of study drugs that are all identical in packaging, labeling, schedule of administration, appearance, and odor.

### **Site staff**

With the exception of any unblinded site staff identified below, all site staff (including study investigator and study nurse) will be blinded to study treatment throughout the study.

Unblinding a single patient at site for safety reasons (necessary for patient management) will occur via an emergency system in place at the site.

Drug product will be supplied in bulk only for the 3 treatment arms in Part A, therefore an unblinded pharmacist who is independent of the study team will be required in order to maintain the blind. Patient treatment allocation can be obtained by the unblinded pharmacist through the IWR system. Appropriate measures must be taken by the unblinded pharmacist to ensure that the treatment assignments are concealed from the rest of the site staff.

There will be fully blinded drug vials for both the active treatment arm and the placebo arm, in Part B of the trial, so unblinded site and clinical staff would not be needed for Part B.

### **Sponsor staff or staff engaged to manage the study**

The following unblinded sponsor staff or staff (such as Contract Research Organization [CRO]) engaged to manage and run the study is required for this study during Part A:

- Unblinded drug accountability monitors
- Unblinded clinical staff managing drug re-supply to site
- Unblinded sample analyst(s) (PK, ADA)

In Part A, unblinded drug accountability monitors are required to review drug accountability, preparation, and allocation remotely. The unblinded monitors will be unblinded through review of source documentation compiled by the unblinded pharmacist, which details treatment allocation to individual patients. These unblinded monitors will also have access to the treatment allocation of the patients through the IWR system.

The following unblinded staff will be applicable to both Part A and Part B:

The external IDMC assessing unblinded results and the independent analysis team (independent statistician, independent programmer) will be allowed to access treatment information for the purpose of creating, reviewing, and assessing unblinded interim results. More details will be provided in an IDMC charter.

An independent pharmacometrician and an independent pharmacokineticist may be unblinded prior to the database lock after all patients complete Day 29 in Part A in order to explore PK

[REDACTED] The pharmacometrician and the pharmacokineticist will work independently and will only disclose results once the database is locked after all patients complete Day 29 in Part A.

### **Unblinding after the primary analysis database lock in Part A**

After the database lock for the primary analysis in Part A, a small unblinded study team will perform the analysis and undertake submission related activities. Treatment assignment will continue to remain blinded to all investigators, site personnel, patients and other study team members until all patients have completed the entire study participation and the final database lock for Part A has occurred.

All unblinded team members will keep randomization lists and data or information that could unblind other study team members confidential and secure until final clinical database lock. Primary analysis results and reports generated prior to the final database lock that would reveal subject-level data will be kept in a secure and restricted area until the end of the study. The detailed procedures for maintaining data integrity after primary analysis database lock will be described in a charter.

Following final database lock all staff may be considered unblinded.

Health authorities will be granted access to unblinded data if needed.

## **6.5 Dose escalation and dose modification**

Investigational or other study treatment dose adjustments are not permitted.

## **6.6 Additional treatment guidance**

### **6.6.1 Treatment compliance**

The start and end date/time of each infusion as well as any infusion interruptions (stop and restart times) will be documented in the eCRF. The prescribed dosage, timing, and mode of administration may not be changed. Any departures from the intended regimen must be recorded in the eCRFs.

Compliance will not be evaluated for this single-dose study.

### **6.6.2 Recommended treatment of adverse events**

For treating patients who deteriorate in their symptoms or conditions related to COVID-19, please refer to [Section 6.2](#). Any infusion-related reactions should follow standard of care (symptomatic treatment), please see [Section 9.1.1](#).

Medication used to treat adverse events (AEs) must be recorded on the appropriate CRF.

### **6.6.3 Emergency breaking of assigned treatment code**

Emergency code breaks must only be undertaken when it is required to in order to treat the patient safely. Blinding codes may also be broken after a patient discontinues treatment due to disease progression if deemed essential to allow the investigator to select the patient's next treatment regimen, and after discussion and agreement with the sponsor. Most often, study treatment discontinuation and knowledge of the possible treatment assignments are sufficient to treat a study patient who presents with an emergency condition. Emergency treatment code breaks are performed using the IRT. When the investigator contacts the system to break a treatment code for a patient, he/she must provide the requested patient identifying information and confirm the necessity to break the treatment code for the patient. The investigator will then receive details of the investigational drug treatment for the specified patient and a fax or email confirming this information. The system will automatically inform the clinical monitor for the site and the study team that the code has been broken.

It is the investigator's responsibility to ensure that there is a dependable procedure in place to allow access to the IRT at any time in case of emergency. The investigator will provide:

- protocol number
- name (if available)
- patient number

In addition, oral and written information to the patient must be provided on how to contact his/her backup in cases of emergency, or when he/she is unavailable, to ensure that un-blinding can be performed at any time.

## **6.7 Preparation and dispensation**

Each study site will be supplied with study drug in packaging as described under investigational and control drugs section.

Drug preparation and dilution according to study arm, prior to administration, is described in the IMP handling and administration manual.

A unique medication number is printed on the study medication label.

### **6.7.1 Handling of study treatment**

Study treatment must be received by a designated person at the study site, handled and stored safely and properly and kept in a secured location to which only the investigator and designated site personnel have access. Upon receipt, all study treatment must be stored according to the instructions specified in the IMP handling and administration protocol.

Clinical supplies are to be dispensed only in accordance with the protocol. Technical complaints are to be reported to the respective sponsor's Quality Assurance.

Study treatment will be prepared by independent pharmacist or qualified site personnel in order to ensure treatment masking. Following labeling and secondary packaging, the MP0420 IMP is supplied as a sterile solution for i.v. infusion. For clinical administration, the required volume of MP0420 IMP will be calculated as defined in the MP0420 clinical trial protocol. Sterile 0.9 % NaCl infusion bags will be used. First, a sodium chloride solution volume equivalent to the required MP0420 IMP volume will be removed from the bag. Second, the required volume of MP0420 IMP will be injected into the bag. The i.v. infusion will then be performed according to standard clinical procedures using a 0.2 µm in-line filter, and followed by an infusion set flush using 25 mL from a fresh 0.9 % NaCl infusion bag.

Medication labels will be in the local language and comply with the legal requirements of each country. They will include storage conditions for the study treatment but no information about the patient except for the medication number.

The investigator must maintain an accurate record of the shipment and dispensing of study treatment in a drug accountability log. Monitoring of drug accountability will be performed by monitors during site visits or remotely and at the completion of the trial.

At the conclusion of the study, and as appropriate during the course of the study, the investigator will return all unused study treatment, packaging, drug labels, and a copy of the completed drug accountability log will be returned to the CRO as part of the final drug accountability filing.

## 7 Informed consent procedures

Eligible patients may only be included in the study after providing (witnessed, where required by law or regulation), Institutional Review Board (IRB)/Independent Ethics Committee (IEC)-approved informed consent.

If applicable, in cases where the patient's representative(s) gives consent (if allowed according to local requirements), the patient must be informed about the study to the extent possible given his/her understanding. If the patient is capable of doing so, he/she must indicate agreement by personally signing and dating the written informed consent document.

Informed consent must be obtained before conducting any study-specific procedures (e.g., all of the procedures described in the protocol). The process of obtaining informed consent must be documented in the patient source documents.

Information about common side effects already known about the investigational drug can be found in the IB. This information will be included in the patient informed consent and should be discussed with the patient during the study as needed. Any new information regarding the safety profile of the investigational drug that is identified between IB updates will be communicated as appropriate, for example, via an investigator notification or an aggregate safety finding. New information might require an update to the informed consent and then must be discussed with the patient.

The following informed consents are included in this study:

- Main study consent for Phase 2 study
- Main study consent for Phase 3 study

Women of child-bearing potential must be informed that taking the study treatment may involve unknown risks to the fetus if pregnancy were to occur during the study and agree that in order to participate in the study, they must adhere to the contraception requirements.

## 8 Visit schedule and assessments

The Assessment Schedule (Part A: [Table 8-1](#), Part B: [Table 8-2](#)) lists all of the assessments when they are performed. All data obtained from these assessments must be supported in the patient's source documentation.

Patients should be seen for all visits/assessments as outlined in the assessment schedule (Part A: [Table 8-1](#), Part B: [Table 8-2](#)) or as close to the designated day/time as possible. Study visits can be performed as home visits by a healthcare provider (e.g., a nurse). Missed or rescheduled visits should not lead to automatic discontinuation. Patients who prematurely discontinue the study for any reason should be scheduled for a visit as soon as possible, at which time all of the assessments listed for the final visit will be performed. At this final visit, AE and concomitant medications will be recorded on the CRF.

When the following assessments are scheduled to be performed at the same time point, the order of priority will be as follows: questionnaire, vital signs, swab/blood sample.

Every effort will be made to take the PK sample at the protocol specified time.

**Table 8-1 Part A: Assessment schedule**

Visit Name	S1 [6]	V1		V2	V3	V4	V5	V6	V7	V8	V9
Study Day	-3 to -1	1		3	5	8 ± 2	15 ± 3	22 ± 4	29 ± 5 (EOS) [7]	61 ± 5	EOS[8] / 91 ±7
		pre-dose	post-dose								
STUDY ENTRY AND GENERAL ASSESSMENTS											
Informed consent	(X)	X									
Inclusion/Exclusion criteria	(X)	X									
Demographics	(X)	X									
Complete medical history	(X)	X									
INVESTIGATIONAL PRODUCT											
Ensovibep (MP0420)/Placebo			X								
SAFETY ASSESSMENTS											
Prior/concomitant medication evaluation	Continuous starting after ICF signature, until 3 months after study medication										
Prior/concomitant hospitalization and procedures	Continuous starting after ICF signature, until 3 months after study medication										
AE evaluation	Continuous starting after ICF signature, until 3 months after study medication										
Local tolerability			X								
Physical examination and vital signs [1]	(X)	X									
General physical appearance and vital signs [1]				X	X	X	X		X		X
Body temperature, respiratory rate, oximetry	(X)	X		X	X	X	X		X		X

Visit Name	S1 [6]	V1		V2	V3	V4	V5	V6	V7	V8	V9
Study Day	-3 to -1	1		3	5	8 ± 2	15 ± 3	22 ± 4	29 ± 5 (EOS) [7]	61 ± 5	EOS[8] / 91 ±7
		pre-dose	post-dose								
Weight	(X)	X									X
Height	(X)	X									
Hematology, chemistry and coagulation safety tests		X		X			X		X	X	X
Pregnancy test in WOCBP [2]	(X)	X									X
Birth Control	Continuous until EOS [3]										
	VIROLOGY & SEROLOGY ASSESSMENTS										
Rapid SARS-CoV-2 antigen test	(X)	X									
SARS-CoV-2 sample (quantitative RT-PCR, mutation analysis)		X		X	X	X	X		X		X
PK blood sample		X	XX [4]	X		X	X		X	X	X
Blood sample for serum biomarkers		X		X		X	X		X		X
	CLINICAL ASSESSMENTS										
Symptom score [5]		X		Daily assessment				X	X		

Visit Name	S1 [6]	V1		V2	V3	V4	V5	V6	V7	V8	V9
Study Day	-3 to -1	1		3	5	8 ± 2	15 ± 3	22 ± 4	29 ± 5 (EOS) [7]	61 ± 5	EOS[8] / 91 ±7
		pre-dose	post-dose								

[REDACTED]; AE=adverse event; EOS=end-of-study; FDA=Food and Drug Administration; ICF=informed consent form; PCR=polymerase chain reaction; PK=pharmacokinetics; PRO=patient-reported outcome; RT=reverse transcriptase; S=screening; [REDACTED]; V=visit; WOCBP=women of child-bearing potential.

1. Vital signs consist of systolic and diastolic blood pressure and heart rate.
2. Urine test with minimum sensitivity 25 mIU/mL for WOCBP in stable contraception for at least 3 months before screening and at EOS. Serum test in other cases, e.g., no previous contraception or unstable (e.g., due to missed days of oral contraceptive or change in contraceptive method).
3. Birth control method will be documented only in source data.
4. Two PK samples: 15 minutes and 90 minutes after end of administration (defined as end of the saline flush).
5. FDA's recommended 14-item symptom assessment ([FDA 2020a](#)) to be used (from which the 8-point score can also be extracted). Options: Daily documentation by patient until Day 15 via PRO-tool, then weekly; or dedicated phone assessment on pre-specified days.
6. Although it is anticipated that most patients will be screened and administered study medication on the same day (Day 1) at Visit 1, patients may have screening procedures performed up to 3 days before study medication administration (Days -3 to -1) and study medication administered on Day 1. The following screening procedures do NOT need to be repeated pre-dose in such case: Informed consent, demographics, complete medical history, height, and weight.
7. Patients who discontinue before Day 29 will complete all V7 (Day 29) assessments as their EOS visit except for the Long-COVID-19 or SF-36 questionnaires.
8. Patients discontinuing between Day 29 and Day 91 to complete V9 (Day 91) assessments as EOS visit.

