#### **8.4.3 Pregnancy and assessments of fertility**

A condom is required for all sexually active male patients to prevent them from fathering a child AND to prevent delivery of study treatment via seminal fluid to their partner. In addition, male patients should not donate sperm for the time period specified above.

All pre-menopausal women who are not surgically sterile will have pregnancy testing at screening and end of study (EOS). Additional pregnancy testing might be performed if requested by local requirements.

**Screening:** Women who have been on stable highly effective contraception in the last 3 months prior to enrollment will have a urine beta-human chorionic gonadotropin ( $\beta$ -HCG) pregnancy test with minimum sensitivity 25 mIU/mL. In other cases, e.g., no previous contraception or unstable (e.g., due to missed days of oral contraceptive or change in contraceptive method), women will have a serum  $\beta$ -HCG pregnancy test.

**EOS:** Urine  $\beta$ -HCG pregnancy test. In the case of a positive test at the EOS, the pregnancy will be reported. The site will contact the participant at least monthly and document the participant's status until the pregnancy has been terminated or until 6 months after the delivery. The outcome of the pregnancy will be reported to the sponsor without delay within 24 hours if the outcome is a serious adverse experience (e.g., death, abortion, congenital anomaly, or other disabling or life-threatening complication to the mother or newborn).

The result of each pregnancy test will be reported on an eCRF.

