## **9 Study discontinuation and completion**

### **9.1 Discontinuation and completion**

#### **9.1.1 Interruption of study drug infusion and study discontinuation**

Study treatment consists of a single dose infusion. In case of interruption of infusion due to AEs, time and relative amount of study drug administered should be recorded in the CRF, as well as restart and end time (as applicable). Adverse event should be captured in appropriate CRF. Treatment of AEs should follow standard of care (symptomatic treatment).

Infusion of study drug must be interrupted or stopped under the following circumstances:

- Patient/guardian decision.
- Suspected hypersensitivity reaction occurs, including any of the following: fever, chills, dyspnea, headache, myalgia, hypotension. Immediate interruption of the infusion to administer study treatment is required in such cases. In case of fever, restart of infusion is permitted under close medical surveillance if the fever subsides with antipyretic treatment. In case of chills, dyspnea, headache or myalgia, restart of infusion is permitted under close medical surveillance if the event was already a noted symptom of COVID-19 at study enrollment and it subsides without treatment within 15 minutes.
- Emergence of any other infusion related reaction: anaphylaxis, angioedema, urticaria, rash, administration site reaction. Immediate interruption of the infusion to administer study treatment is required in such cases. Restart of infusion is not recommended.

Patients who discontinue study treatment or who decide they do not wish to participate in the study further should NOT be considered withdrawn from the study UNLESS they withdraw their consent (see [Section 9.1.2](#) ‘Withdrawal of Informed Consent’ section). **Where possible, they should return for the assessments indicated** in the Assessment Schedule. If they fail to return for these assessments for unknown reasons, every effort (e.g., telephone, e-mail, letter) should be made to contact the patient/pre-designated contact as specified in the lost to follow-up section. This contact should preferably be done according to the study visit schedule.

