### **9.1.2 Withdrawal of informed consent**

Patients may voluntarily withdraw consent to participate in the study for any reason at any time. Withdrawal of consent occurs only when a patient:

- Does not want to participate in the study anymore,  
and
- Does not want any further visits or assessments,  
and
- Does not want any further study related contacts.

In this situation, the investigator should make a reasonable effort (e.g., telephone, e-mail, letter) to understand the primary reason for the patient's decision to withdraw his/her consent and record this information.

Legal framework of certain countries does not require consent to the use of personal and coded data. However, patients in these countries do retain the right to object to the further use of their personal data.

Study treatment must be discontinued and no further assessments conducted, and the data that would have been collected at subsequent visits may not be collected and will be considered missing.

Further attempts to contact the patient are not allowed unless safety findings require communicating or follow-up.

All efforts should be made to complete the assessments prior to study discontinuation. A final evaluation at the time of the patient's study discontinuation should be made as detailed in the assessment table.

All research results (data) that have already been collected for the study evaluation will continue to be used.

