#### **9.1.5 Early study termination by the sponsor**

The study can be terminated by the sponsor at any time.

Reasons for early termination

- Unexpected, significant, or unacceptable safety risk to patients enrolled in the study
- Decision based on recommendations from applicable board(s) after review of safety and efficacy data
- Discontinuation of study drug development

In taking the decision to terminate, the sponsor will always consider patient welfare and safety. Should early termination be necessary, patients must be seen as soon as possible and treated as a prematurely withdrawn patient. The investigator shall be informed of additional procedures to be followed in order to ensure that adequate consideration is given to the protection of the patient's interests. The investigator or sponsor depending on local regulation will be responsible for informing IRBs/IECs of the early termination of the trial.

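### Part A schedule: the exit visit for patients who leave before Day 29 omits the pregnancy test that the protocol requires at end of study

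*Protocol*

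**What the plan says.** The requirement appears twice in the protocol. Section 8.4.3 states: "All pre-menopausal women who are not surgically sterile will have pregnancy testing at screening and end of study (EOS", and then specifies a urine beta-HCG test at EOS. A positive result is to be reported and the pregnancy followed up. Footnote 2 of Table 8-1, attached to the pregnancy-test row, reads: "Urine test with minimum sensitivity 25 mIU/mL for WOCBP in stable contraception for at least 3 months before screening and at EOS".

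Two further footnotes define which visit is the EOS visit for patients who leave early:

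- Footnote 7, attached to the EOS label on V7: "Patients who discontinue before Day 29 will complete all V7 (Day 29) assessments as their EOS visit". The Long-COVID-19 and SF-36 questionnaires are the only exceptions.
- Footnote 8: "Patients discontinuing between Day 29 and Day 91 to complete V9 (Day 91) assessments as EOS visit".

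The pregnancy-test row of Table 8-1 is marked at S1 (optional), V1 pre-dose and V9, and nowhere else.

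**The concern.** The text requires a pregnancy test at EOS, and footnote 7 makes V7 the EOS visit for anyone leaving before Day 29. The V7 column does not list the test, and footnote 7 does not add it. So the schedule and the text disagree for this group.

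The table is where sites are told to look. Section 9.1.2 says that a final evaluation at "study discontinuation should be made as detailed in the assessment table". The rationale for the global amendment of 19 October 2021 says the EOS footnote was introduced so that the right assessments are done for the timing of a patient's last visit. On this test the footnote does not achieve that.

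What is at stake is detection of a pregnancy at exit. The protocol acknowledges unknown fetal risk (Sections 4.5 and 7) and requires contraception for 11 weeks after dosing (Section 5.2, criterion 10). For a woman who withdraws consent, the exit visit may be her last study contact, because Section 9.1.2 bars further contact unless a safety finding calls for it. The 24-hour reporting duty in Section 10.1.5 still holds, but it helps only if the pregnancy is known.

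**Working it through.** The plan gives no figure to reproduce. The check is a reading of the grid against the text, followed by simple arithmetic on time and numbers.

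**1. Is the empty V7 cell real, or an effect of text extraction?** The pregnancy-test row has 12 fields, a label plus 11 visit columns, the same as the header row. Other rows with the same field count place their marks at V7 correctly:

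| Row of Table 8-1 | Visits marked |
|---|---|
| Pregnancy test | S1, V1 pre-dose, V9 |
| Safety laboratory tests | V1 pre-dose, V2, V5, V7, V8, V9 |
| SARS-CoV-2 sample | V1 pre-dose, V2, V3, V4, V5, V7, V9 |
| Body temperature, respiratory rate, oximetry | S1, V1 pre-dose, V2, V3, V4, V5, V7, V9 |

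The columns are aligned, so the empty V7 cell does not look like a shifted column.

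**2. Which patients are affected?**

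| Time of leaving | EOS visit | Test required by 8.4.3 and footnote 2 | Test marked in the grid |
|---|---|---|---|
| Before Day 29 | V7 (footnote 7) | Yes | No |
| Day 29 to Day 91 | V9 (footnote 8) | Yes | Yes |
| Completes the study | V9 | Yes | Yes |

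Only the first row is inconsistent.

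**3. How large is that group?** Section 9.1.1 says patients who stop treatment or no longer wish to take part "should NOT be considered withdrawn from the study UNLESS they withdraw their consent". Where possible they return for scheduled visits, and so reach the V9 test. Two kinds of patient remain, both women of child-bearing potential before Day 29: those who withdraw consent but accept a final evaluation, and those still in follow-up if the sponsor ends the study early, when Section 9.1.5 says "patients must be seen as soon as possible and treated as a prematurely withdrawn patient". The documents give no dropout rate and no number of women of child-bearing potential, so no count can be derived.

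**4. Contraception time left at exit.** The period is 11 × 7 = 77 days from dosing on Day 1. Days left on leaving at Day d = 77 − (d − 1):

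- Day 2: 77 − 1 = 76
- Day 8: 77 − 7 = 70
- Day 15: 77 − 14 = 63
- Day 28: 77 − 27 = 50

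**5. How many Part A patients can a correction still reach?** The amendment reports 381 treated, and Section 3 plans at least 400. That leaves 400 − 381 = 19 of the planned minimum, assuming every randomized patient is dosed, plus those already treated but not yet at Day 29.

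**The case against.** The strongest reply is that nothing is missing. Section 8.4.3 and footnote 2 already require the test at EOS, and the table includes its footnotes. A site would have to apply footnote 7 and overlook footnote 2 in the same list. This is true, and it is why the point is an inconsistency and not an absent requirement. It does not make the V7 column correct.

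Second, the opening of Section 8 tells early leavers to have the assessments listed for the final visit. If that means V9, the test is included. But the sentence does not name a visit, and footnote 7 is more specific and names V7.

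Third, EOS could mean Day 91 only. Section 10.1.5 equates end of study with 13 weeks after dosing when it discusses partners' pregnancies, and SAP Table 2.1-2 attaches the EOS label to Day 91 alone. On that reading the grid would already be right. However, the V7 header in Table 8-1 carries the EOS label, and footnote 7 calls V7 the EOS visit for these patients, so this reading cannot be squared with the protocol's own schedule.

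The limits on size do stand. Section 9.1.2 defines withdrawal as wanting no further visits, so few who withdraw will attend one. An exit test cannot detect very recent or later conceptions, so the 76 to 50 days describe the woman's situation and do not measure the test's benefit.

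**Conclusion.** The concern holds. As written, the grid and footnote 7 of Table 8-1 omit, for women of child-bearing potential leaving Part A before Day 29, a pregnancy test that Section 8.4.3 and footnote 2 require.

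It is a minor safety-schedule error, worth at most one urine test per affected woman. It does not affect the primary analysis, sample size, type I error or the duty to report known pregnancies. No number of missed tests, undetected pregnancies or exposure-related risk is claimed. The conclusion rests on reading EOS as the patient's own exit visit, as the V7 label and footnote 7 do.

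The Table 8-2 grid is not in the text available for this review, so no defect is claimed for Part B. The change log for the same amendment says the EOS assessments were revised in both tables, which is reason enough to check the other one, given that Part B plans 1717 patients.

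**What to change.** In Table 8-1, mark the urine pregnancy test in the V7 column, conditional on V7 being the patient's EOS visit, and name the test in footnote 7. Check Table 8-2 for the same omission and correct it if present before Part B opens.

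The cost is one conditional mark and one phrase. In practice it means one urine test for each woman of child-bearing potential who leaves before Day 29 and attends an exit visit, and Section 8.4.3 already requires that test.
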